A randomized, double-blind, controlled factorial clinical trial of edetate disodium-based chelation and high-dose oral vitamins and minerals to prevent recurrent cardiac events in diabetic patients with a prior myocardial infarction.

**REVISION HISTORY**

February 8, 2016 (Original Version Date)  
July 1, 2016  
May 18, 2017  
November 1, 2019  
May 6, 2021

## PRÉCIS

### Study Title

Trial to Assess Chelation Therapy 2 (TACT2).

A randomized, double-blind, controlled factorial clinical trial of edetate disodium-based chelation and high-dose oral vitamins and minerals to prevent recurrent cardiac events in diabetic patients with a prior myocardial infarction (MI).

### Objectives

TACT2 is being carried out to replicate TACT, which found a reduction of recurrent cardiovascular events in post-MI diabetic patients receiving edetate disodium-based chelation therapy.

The primary objective of TACT2, therefore, is to determine if the chelation-based strategy increases the time to the first occurrence of any of the components of the TACT2 primary endpoint: all-cause mortality, myocardial infarction, stroke, coronary revascularization, or hospitalization for unstable angina compared to the placebo chelation strategy.

The secondary objectives of TACT2 are to determine:

1. if the chelation-based strategy reduces the overall rate of occurrence of the events which define the primary TACT2 endpoint: all-cause mortality, myocardial infarction, stroke, coronary revascularization, or hospitalization for unstable angina events compared to placebo chelation strategy.
2. if the chelation-based strategy increases the time to the first occurrence of a composite endpoint: cardiovascular mortality, recurrent myocardial infarction, or stroke compared to placebo chelation strategy.
3. if the chelation-based strategy increases the time to all-cause mortality compared to placebo chelation strategy.

### Design and Outcomes

TACT2 is a 2x2 factorial trial testing 40 weekly edetate disodium-based chelation infusions and twice-daily high-dose oral multivitamins and multiminerals (OMVM) in a placebo-controlled design.

The primary endpoint is a composite of all-cause mortality, myocardial infarction, stroke, coronary revascularization, or hospitalization for unstable angina. All randomized patients will be followed until the end of the trial.

The secondary endpoints for TACT2 include the following:

**Total number of CV events:** This endpoint will include all CV events from randomization to the end of the study.

**All-cause mortality:** All-cause mortality is a secondary endpoint for the trial, based upon its importance and the observed 43% relative risk mortality reduction by chelation alone ( $P=0.011$ ) in the diabetic subgroup of TACT.

**Composite of cardiovascular mortality, recurrent myocardial infarction, or stroke:**

This composite secondary endpoint captures serious, irreversible, ischemic events. Chelation treatment led to a 40% relative reduction in risk ( $P=0.017$ ) in this endpoint in the diabetic subgroup of TACT.

Exploratory analyses, defined as those seeking to confirm a signal of benefit observed in TACT, or to develop mechanistic hypotheses for benefits of chelation expected in TACT2, include:

- i. Analysis of the primary endpoint in patients receiving OMVM compared with oral placebo
- ii. Analysis of the primary endpoint in patients receiving active chelation + active OMVM, compared with placebo chelation + placebo OMVM
- iii. Analysis of markers of severity of diabetes (fasting glucose, HbA1c, microalbuminuria) throughout the infusion regimen
- iv. Analysis of lead and cadmium levels at multiple times during the infusion regimen
- v. Collection of biospecimens for the constitution of a biorepository to permit future analyses yet to be conceived

**Sample Size and Population**

TACT2 has enrolled 1000 diabetic patients 50 years of age or older with a prior MI and a serum creatinine of 2.0 mg/dL or less. Patients will be randomly allocated (1:1:1:1) to 4 factorial groups, each with approximately 250 patients. TACT2 will use a simple randomization scheme. The four treatment groups are:

1. Active chelation + active OMVM
2. Active chelation + placebo OMVM
3. Placebo chelation + active OMVM
4. Placebo chelation + placebo OMVM

The study is targeting a population consisting of 40% women and 18% minority subjects.

## **1. STUDY OBJECTIVES**

TACT2 is being carried out to replicate TACT, which found a reduction of recurrent cardiovascular events in post-MI diabetic patients receiving edetate disodium-based chelation therapy.

### **1.1 Primary Objective**

The primary objective of TACT2, therefore, is to determine if the chelation-based strategy increases the time to the first occurrence of any of the components of the TACT2 primary endpoint: all-cause mortality, myocardial infarction, stroke, coronary revascularization, or hospitalization for unstable angina compared to the placebo chelation strategy.

### **1.2 Secondary Objectives**

The secondary objectives of TACT2 are to determine:

1. if the chelation-based strategy reduces the overall rate of occurrence of the events which define the primary TACT2 endpoint: all-cause mortality, myocardial infarction, stroke, coronary revascularization, or hospitalization for unstable angina events compared to placebo chelation strategy.
2. if the chelation-based strategy increases the time to the first occurrence of a combined secondary endpoint: cardiovascular mortality, myocardial infarction, or stroke compared to placebo chelation strategy.
3. if the chelation-based strategy increases the time to all-cause mortality compared to placebo chelation strategy.

Exploratory analyses, defined as those seeking to confirm a signal of benefit observed in TACT, or to develop mechanistic hypotheses for benefits of chelation expected in TACT2, include:

- i. Analysis of the primary endpoint in patients receiving OMVM compared with oral placebo
- ii. Analysis of the primary endpoint in patients receiving active chelation + active OMVM, compared with placebo chelation + placebo OMVM
- iii. Analysis of markers of severity of diabetes (fasting glucose, HbA1c, microalbuminuria) throughout the infusion regimen
- iv. Analyses of lead and cadmium in blood and urine to:
  - a. Compare the change in metal internal dose (blood lead and urine cadmium) in TACT2 participants, from infusion 1 to infusion 40 (or 1 year) in the active versus placebo infusion arms.
  - b. Evaluate whether higher screening metal internal dose (blood lead and urine cadmium) and the extent of depletion of those stores identify patients more likely to benefit from chelation.
- v. Collection of biospecimens for the constitution of a biorepository to support future

mechanistic work. Samples of blood (plasma and buffy coat) and urine will be stored at -80°C in a secured biorepository to ensure their availability for the evaluation of future hypotheses that will be guided by the results of the trial.

The above metal collections and biorepository will serve to support analyses to determine whether post-infusion urine metal measurements, alone and in comparison to the corresponding pre-infusion measurements, have clinical significance for predicting outcomes and clinical benefit of chelation; and whether the suite of additional metal levels measured in blood and urine by inductively coupled plasma mass multi-element analytic technique, some of which are not chelated by edetate disodium, have clinical (prognostic) significance in preliminary testing

## **2. BACKGROUND AND RATIONALE**

### **2.1 Background on Condition, Disease, or Other Primary Study Focus**

Chelation treatment was first reported to have clinical benefits in symptomatic CAD patients in 1956 and 1961. In the early 1960s, however, following a reappraisal by Kitchell, only alternative medicine practitioners continued to use chelation for prevention of complications of atherosclerosis based on their positive anecdotal experiences. Ultimately, academic authors published 3 small studies with an aggregate of <300 patients and concluded that there was no benefit from chelation for surrogate endpoints such as time to claudication or angina. Yet these studies were too small and of too short a duration to exclude a small or moderate effect on clinical endpoints. Despite recommendations against the practice of chelation by numerous professional medical associations, patients continued to seek, and some practitioners to administer, chelation therapy for a variety of medical conditions.

The National Institutes of Health (NIH) funded TACT in 2002. The design was a 2X2 factorial, randomly allocating patients to intravenous edetate disodium-based chelation or placebo, and high-dose oral multivitamins and multiminerals or oral placebo. Standard chelation practice in the community also included the addition of oral supplements to the intravenous treatments; hence the factorial design. There were 1708 post-MI patients enrolled in 134 sites and 55,222 infusions administered as part of TACT.

In guideline-treated post-MI patients, chelation alone led to an 18% reduction in a combined cardiovascular endpoint (HR 0.82 (0.69, 0.99) P=0.035, 7-year NNT=18). Patients with diabetes had dramatic benefit from IV chelation (HR 0.59, (0.44, 0.79), P=0.0002, 5-year NNT=6.5). An analysis of the factorial groups demonstrated that the strategy of intravenous chelation plus OMVM yielded a 26% reduction over double placebo (HR 0.74 (0.57, 0.95), P=0.016, 5-year NNT=12). The effect size and the potential for an impact on public health and health care financing were the primary reasons for the Investigators' desire to move forward with TACT2, in this case focusing on the patients in whom the greatest benefit had been observed (Table 1). The investigators also felt that inclusion of an exploratory mechanistic component to the clinical trial would be desirable. TACT2, therefore, if positive, will be a confirmatory

second trial of edetate disodium-based chelation for patients with established coronary disease, and should provide the groundwork for mechanistic hypotheses – that ubiquitous pro-oxidant toxic metals, especially lead and cadmium, are associated with recurrent coronary events.

**Table 1.** Summary of Results from TACT

Population*	Endpoint**	Treatment comparison	Event rate relative reduction	p-value	5-year NNT
Overall	Primary	EDTA vs. placebo	18%	0.035	18
Overall	Primary	EDTA + OMVM vs. placebo + placebo	26%	0.016	12
Diabetes	Primary	EDTA vs. placebo	41%	0.0002	6.5
Diabetes	Death	EDTA vs. placebo	43%	0.011	12
Diabetes	Primary	EDTA + OMVM vs placebo + placebo	51%	<0.001	5.5

\* Post-MI, age  $\geq$  50 years, creatinine  $\leq$  2.0; \*\* time-to-event. Primary endpoint: time to death, MI, stroke, coronary revascularization, and hospitalization for angina; MVM: Multivitamins & Multiminerals; NNT: number needed to treat to prevent an event.

The OMVM versus placebo comparison demonstrated an 11% relative reduction in risk that was not statistically significant. Yet, as can be seen above, there appears to be a numerical, but not statistically significant, signal of benefit from OMVM, reducing the hazard ratio by about 10% each time OMVM is added to the chelation infusion. The TACT vitamins included higher doses of the individual OMVM components than previously used in other trials, and the non-significant signal of potential benefit challenges current opinions on vitamin use for cardiovascular disease. Thus, the TACT2 protocol replicates the 2x2 factorial design initially used in TACT.

One of the two factors in the 2x2 factorial design – OMVM – is not incorporated in a primary or a secondary objective of the trial, and appears only in exploratory analyses. The reasons for this are as follows:

1. A factorial design will allow us to discern whether there is replication of the effect of OMVM on clinical events.
2. If there is an effect, the complex chelation strategy with 38 components will likely be linked, to the benefit of intravenous chelation, and new lines of research into the vascular effects of ultra-high dose oral anti-oxidant mixtures given new life. This will apply even if the effect is numerical and qualitative, and not necessarily statistically significant. Observing the same signal of benefit in 2 studies would be very important.
3. The most likely result, given the weight of prior vitamin research, is that there will be no effect of OMVM. If this is true, then the 28 oral components can be unlinked from the chelation strategy. This will improve patient compliance and, for the cardiology community, reduce barriers to acceptance and implementation.
4. There will be no statistical cost (assuming additive treatment effects) to the chelation vs placebo infusion comparison, which in TACT (diabetes) had a HR of 0.59. The proposed sample size will provide 85% power to detect a HR of 0.70 for the primary endpoint, and 95% power to detect a HR of 0.65, both conservative estimates based on TACT results. In summary, if vitamins are not an essential part of the effectiveness of the TACT regimen, being able to clarify

*this in TACT2 will allow FDA to consider the approval of chelation alone and will make the treatment significantly easier to administer clinically. At the same time, if the relationships in the factorial comparisons of TACT can be reproduced in TACT2 for both chelation and vitamins, we will have opened up two major new research areas rather than just one.*

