**OMVM/placebo:** The OMVM consists of 3 caplets, twice daily for a total intake of vitamin A 25000 IU, vitamin C 1200 mg, vitamin D3 100 IU, vitamin E 400 IU, vitamin K1 60 µg, thiamin 100 mg, niacin 200 mg, vitamin B6 50 mg, folate 800 µg, vitamin B12 100 µg, biotin 300 µg, pantothenic acid 400 mg, calcium 500 mg, iodine 150 µg, magnesium 500 mg, zinc 20 mg, selenium 200 µg, copper 2 mg, manganese 20 mg, chromium 200 µg, molybdenum 150 µg, potassium 99 mg, choline 150 mg, inositol 50 mg, para-aminobenzoic acid 50 mg, boron 2 mg, vanadium 35 µg, citrus bioflavonoids 100 mg. Placebo caplets consist of microcrystalline cellulose, stearic acid, croscarmellose sodium, silica and magnesium stearate. OPADRY® II complete film white coating, magnesium stearate and vanilla flavor are used to coat both active and placebo pills. These caplets are taken for the entire duration of the study.

**Low-dose vitamins:** The low-dose supplements are taken by all patients to prevent any deficiency syndromes from chelation of essential minerals or vitamins. They consist of: vitamin B6, chromium, copper, manganese, and zinc. As was done in TACT, all patients will receive a low-dose regimen consisting of a single pill to be taken during the infusion regimen, stopping at 1 year at the latest. The low-dose regimen consists of: vitamin B6 25 mg, zinc 25 mg, copper 2 mg, manganese 15 mg, and chromium 50 µg.

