### **9.2 Sample Size and Randomization**

Participants will be randomized in a 1:1:1:1 allocation ratio using simple randomization. The study was originally designed to enroll a total of 1200 participants with a minimum follow-up of 12 months. The DSMB conducted a blinded review of enrollment aggregate event rates, and projected event rates in July 2019. Following this blinded review, the

DSMB recommended a reduction in the target sample size to 1100 participants and an increase in the minimum follow-up from 1 year to approximately 2.5 years. Due to slowed enrollment related to the COVID-19 pandemic, in the fall of 2020, the DSMB and the NIH leadership agreed to a proposal to complete enrollment by 12/31/2020 with an allowance to follow the study participants until there are enough primary endpoint events to maintain 85+% power.

Several design factors and research objectives have been considered in developing an appropriate sample size for the TACT2 study. First, patient enrollment and follow-up has been determined so there would be a sufficient number of endpoints to provide a high degree of confidence for testing the primary hypothesis. Second, the statistical power for secondary endpoints has been considered. Finally, the sample size has been determined to provide a reasonable level of confidence for detecting clinically important differences in outcome between treatment strategies even if current projections of event rates and hypothesized differences in clinical outcomes between the treatment groups prove to be optimistic.

Table 3 shows the required number of endpoint events to have 80% to 90% power with hazard ratios varying from 0.50 to 0.75. The two factors (EDTA chelation and OMVM) are assumed to be additive for the sample size calculations. Based on TACT we anticipate a hazard ratio of 0.70 (active chelation vs. placebo chelation) to determine the sample size requirements. This hazard ratio assumption is very conservative compared to the observed effect in TACT. Assuming a two-sided 0.05 type I error rate and approximately 5% consent withdrawal or loss-to-follow-up per year, the final sample size of 1000 participants will provide approximately 85% power to detect a hazard ratio of 0.70 for the primary endpoint of time to all-cause mortality, myocardial infarction, stroke, coronary revascularization, or hospitalization for unstable angina comparing active chelation vs. placebo chelation.

Table 3. Required number of events						

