1.1 Study Design

The Trial to Assess Chelation Therapy 2 (TACT2) is a randomized, double blinded, placebo-controlled 2x2 factorial clinical trial. The study treatments are edetate disodium-based chelation (weekly infusion for 40 weeks) and high-dose oral multivitamins and multi-minerals (OMVM) (twice daily for up to 5 years). Subjects with diabetes mellitus with a prior myocardial infarction (MI) are recruited from participating sites in the US and Canada and randomized in a 1:1:1:1 fashion to 4 groups:

- i. Active chelation + active OMVM
- ii. Active chelation + placebo OMVM
- iii. Placebo chelation + active OMVM
- iv. Placebo chelation + placebo OMVM.

Patients will be followed for clinical events until the earlier of database lock or five years from randomization. Clinical outcomes will be collected by study sites at each infusion visit and by the DCRI Call Center at month 6 and 12, and every 4 months afterwards with the last assessment at month 60.

TACT2 is an event driven trial with a plan to continue until at least 282 primary endpoint events are identified. The original planned sample size was 1200 participants. The sample size was later modified to 1100. The final enrollment is 1000, but with an increased follow-up time to preserve statistical power. More details on sample size and power calculation are included later in the SAP.

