3.2.1 Primary Analysis

The primary objective is to determine if the chelation-based strategy increases the time to composite endpoint compared with the placebo chelation strategy. The primary composite endpoint will be analyzed using a Cox proportional hazards regression model of time from randomization to the first occurrence of all-cause mortality, MI, stroke, coronary revascularization, or hospitalization for unstable angina.

The primary analysis will be based on a Cox model which includes indicator variables for the active chelation as the primary variable of interest and active OMVM groups, age, sex, and baseline insulin use as covariates. Age will be included in the model in the form of cubic splines using three knots at 10th, 50th, and 90th percentiles. Two separate manuscripts will explore the effect of active OMVM and the effects of chelation by OMVM.

The chelation treatment effect will be summarized using hazard ratios and associated 95% CIs. A hazard ratio of < 1 would suggest a benefit for the chelation-based therapy. Kaplan Meier survival estimates will be constructed based on the time from randomization to the first

primary event occurrence. Events occurring after withdrawal of consent or informed consent expiration will be censored.

The OMVM treatment effect from the Cox model will be estimated using the Cox model described above. A hazard ratio of < 1 would suggest a benefit for OMVM treatment. Given the focus on chelation therapy, the interpretation of the OMVM treatment effect will be considered exploratory. A full set of analyses of the 2x2 design will be reported in a separate manuscript.

Four interim analyses were conducted at 25%, 40%, 60%, and 80% of expected information using a Haybittle-Peto-type boundary for efficacy (i.e. $p \leq 0.001$, $Z=3$). For this reason, the adjusted two-sided significance level for the final analysis is 0.05 (i.e., the corresponding critical value, $Z = -1.96$).

Formal statistical hypothesis testing will follow a hierarchy based on statistical significance of the prior endpoint. If the prior endpoint is statistically significant at the 0.05 level, the next endpoint's p-value will be tested for significance. The outcome hierarchy will be evaluated as follows:

- 1) Primary composite outcome
- 2) Secondary all-cause mortality outcome (with conservative censoring)
- 3) Secondary composite outcome of cardiovascular mortality, MI, or stroke

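### The reasons given for keeping the OMVM factor attach consequences both to a non-significant signal and to a null result, and about 282 events cannot support either

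*Protocol*

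**What the plan says.** Protocol 2.1 gives four numbered reasons for keeping a factor that belongs to no primary or secondary objective.

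- **Item 1:** the factorial design will show whether the OMVM effect on clinical events replicates.
- **Item 2:** if there is an effect, the 38-component strategy will probably be treated as linked. The protocol adds: "This will apply even if the effect is numerical and qualitative, and not necessarily statistically significant". It regards the same signal in two studies as very important.
- **Item 3:** no effect is thought the most likely result. "If this is true, then the 28 oral components can be unlinked from the chelation strategy".
- **Item 4, closing sentences:** if vitamins are not essential to the regimen, clarifying "this in TACT2 will allow FDA to consider the approval of chelation alone". The power figures in this item (85% at HR 0.70, 95% at HR 0.65) are for chelation.

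SAP 3.2.1 estimates the OMVM effect from the primary Cox model, calls its interpretation exploratory, and adds: "A hazard ratio of < 1 would suggest a benefit for OMVM treatment". The full 2x2 analysis goes to a separate manuscript.

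Neither document gives a minimum effect, a margin for absence of effect, or power for OMVM on clinical events. The general power statement for exploratory endpoints in Protocol 9.2 is a t-test calculation in standard-deviation units, so it does not cover this comparison.

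Protocol 5.1 also describes a separate low-dose pill: "The low-dose supplements are taken by all patients to prevent any deficiency syndromes from chelation of essential minerals or vitamins".

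**The concern.** The OMVM factor is justified by the conclusions it will permit, so the design should be able to deliver them. The 282-event target was set for a chelation hazard ratio of 0.70. The OMVM effect to be replicated is an 11% reduction, which was itself not significant in TACT.

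Without a criterion, one estimate can be read either way. An OMVM HR of 0.95 is a numerical benefit under item 2, and it could also be presented as the absence of an effect under item 3. The choice would then be made after seeing the data.

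Two things are at stake: which components the regimen is said to need, and a regulatory argument that rests on the answer. Protocol 2.1 itself faults the early chelation studies for being too small and too short to rule out small or moderate effects on clinical endpoints. Item 3 needs this trial to rule out such an effect for OMVM.

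**Working it through.** **Inputs**

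- Events: "TACT2 is an event driven trial with a plan to continue until at least 282 primary endpoint events are identified" (SAP 1.1). Protocol 9.4 says roughly 280. The projections in SAP 1.2 and Appendix I run from 235 to 308.
- Allocation: "Participants will be randomized in a 1:1:1:1 allocation ratio using simple randomization" (Protocol 9.2), which is 1:1 on the OMVM margin.
- Test level: "Assuming a two-sided 0.05 type I error rate and approximately 5% consent withdrawal or loss-to-follow-up per year" (Protocol 9.2).
- OMVM effect in TACT: an 11% reduction, HR 0.89 (Protocol 2.1). The same section also describes about 10% when OMVM is added to chelation, HR 0.90.

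**Step 1. Reproduce the plan's own figure.** Events = 4 × (1.96 + 1.036)² / (ln 0.70)² = 4 × 8.98 / 0.1272, or 283 after rounding up. Protocol Table 3 gives 282. The same formula reproduces all 18 cells of that table within one event. Power at 282 events is 85% for HR 0.70 and 95% for HR 0.65, as stated for chelation.

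**Step 2. Precision for OMVM.** SE(log HR) = 2/√282 = 0.119, assuming 1:1 on the margin and no interaction with chelation.

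**Step 3. Power for the TACT effect.** ln(0.89) = −0.1165, and 0.1165/0.119 = 0.98. Power = Φ(0.98 − 1.96) = Φ(−0.98) = 16%. It is 14% to 17% over 235 to 308 events, and 14% for HR 0.90 at 282 events. For 80% power at HR 0.89, events = 4 × (1.96 + 0.84)² / (0.1165)², about 2,312. That is 2,312/282, or about 8 times the plan.

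**Step 4. Apparent replication when OMVM does nothing.**

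- P(observed HR ≤ 0.89) = Φ(−0.98) = 16% (15% to 19% over 308 to 235 events).
- P(observed HR < 1) = 50% at any event count.

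**Step 5. What a null estimate excludes.**

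- At an observed HR of 1.00, the 95% CI is exp(±1.96 × 0.119) = 0.79 to 1.26. It rules out only reductions larger than about 21% (1 − 0.79). The interval is 0.77 to 1.29 with 235 events and 0.80 to 1.25 with 308.
- The lower limit passes 0.89 only if the observed HR exceeds 0.89 × 1.263 = 1.12. With no true effect, that has a 16% chance.
- At an observed HR of 0.95, the 95% CI is 0.75 to 1.20, which contains both 0.89 and 1.

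**Step 6. A larger assumed effect.** The documents give no OMVM-only estimate in diabetes. A crude ratio from Protocol Table 1 (51% and 41% reductions) is 0.49/0.59 = 0.83. It mixes two different comparisons and serves only for scale. Power there is Φ(0.186/0.119 − 1.96) = Φ(−0.40), about 34%, and 0.83 also lies inside the interval at HR 1.00.

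**The case against.** **The status of the OMVM comparison.** OMVM is in no primary or secondary objective, is absent from the SAP testing hierarchy, is seen by the DSMB for safety only, and is called exploratory in Protocol 9.6 and SAP 3.2.1. Section 2.1 is rationale in tentative language, and unlinking is conditional on there truly being no effect. All of this stands, and it limits the weight of the point. It does not remove it: the same section calls a repeated signal very important and attaches a regulatory consequence, without saying what would count as a signal or as its absence.

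Three stronger readings are tempting, and the documents do not support them.

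- **Any OMVM hazard ratio below 1 counts as replication, so the rule is a coin flip.** Protocol 2.1 never says this. It speaks of the same signal, after describing one of about 10% to 11%; for an HR of 0.89 or lower the false-positive figure is 16%. The SAP sentence on HR < 1 is a direction convention, used also for chelation, the recurrent-event models and, for the mean posterior hazard ratio, the Bayesian analysis.
- **A non-significant result triggers unlinking, which would happen about 84% of the time if HR 0.89 were true.** The protocol does not equate non-significance with no effect. Item 2 says close to the opposite.
- **A null result says nothing about the five components in the low-dose pill (B6, zinc, copper, manganese, chromium).** That pill stops by 1 year while OMVM continues for the whole study. During infusions OMVM is taken on top of it, for zinc 20 + 25 = 45 mg against 25 mg. The contrast is diluted early but not removed.

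It is also fair that 0.89 is a debatable margin, being a non-significant estimate from TACT as a whole. Using it would require an observed HR above about 1.12 before OMVM could be called unnecessary.

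**Conclusion.** The point holds in a limited form. Protocol 2.1 claims that the factorial design can discern replication of the OMVM effect, accepts a non-significant effect as consequential, and lets a null result unlink the oral components. At about 282 events, power for HR 0.89 is about 16%, and an estimate of exactly 1.00 leaves 0.79 to 1.26 open. Following the text could therefore give an unsupported conclusion in either direction.

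This rests on a normal approximation without covariates, equal allocation on the OMVM margin, no interaction, and 0.89 as the TACT effect. The conclusion does not change over 235 to 308 events or at HR 0.90. Even at the crude 0.83, power is only about one in three.

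It is a fault in how OMVM results are to be interpreted. It does not affect the design, power or analysis of the chelation comparison.

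**What to change.** **Protocol 2.1.** Delete "This will apply even if the effect is numerical and qualitative, and not necessarily statistically significant". State the OMVM precision: about 16% power at HR 0.89, and a 95% CI of about 0.79 to 1.26 around an estimate of 1.00. Make the unlinking sentence conditional on the confidence interval excluding a benefit that the sponsor names and justifies before the OMVM estimate is seen.

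**SAP 3.2.1 and the plan for the OMVM manuscript.** State that:

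- the OMVM hazard ratio is reported with its 95% CI;
- replication is claimed only if the interval excludes 1 in favour of OMVM;
- an interval containing both 1 and the prespecified benefit is inconclusive;
- the HR < 1 sentence shows direction only.

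In both places, note that during the infusion period (up to 1 year) the contrast is OMVM on top of the low-dose supplement.

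**Cost.** Wording only, with no change to data collection or the chelation analysis. Under Protocol 7, an amendment that is more than administrative needs DSMB and IRB approval. If that is impractical, the criteria can go in the SAP and the manuscript plan alone. The real downside is that OMVM will most likely be reported as inconclusive, which is what this number of events can support.
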